6.5. Follow-up of patients switched to non-participating physicians

If for any reason (eg, relocation, insurance change) a patient switches to a physician who is not participating in the study, the patient will be discontinued from the study. The enrolling physician will complete a follow up questionnaire with the last available clinical data and the subject summary module of the questionnaire. If the patient does not withdraw consent to participate in the study, an attempt will be made to ascertain the vital status of the patient as mentioned in Section 6.4 for patients lost to follow up.

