### **3. INTERIM ANALYSES, FINAL ANALYSES AND UNBLINDING**

Periodic review of the study progress and assessment of collected data will be conducted by the Scientific Steering Committee (SSC) once in every six months. The data to be reviewed by the Steering Committee will be outlined in a separate analysis plan. In addition, yearly progress reports will be provided to the regulatory agencies throughout the duration of the study. The analyses as outlined in Section 8.2 will be adopted for reporting these results. There are no formal stopping rules for the study; however, the SSC may recommend stopping the study for safety issues at any time.

Full final analysis will follow the official database release. Since this is an open label study, no formal un-blinding of the randomization is needed.

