#### 4.2.2. Estimation of follow up time

Patients enrolled in the maraviroc-exposed group: all follow up time accrued in the study will be contributed to the “maraviroc-exposed” group regardless of the actual duration of maraviroc use.

Patients enrolled in the maraviroc-unexposed group: all follow up time accrued in the study will be contributed to the “maraviroc-unexposed” group regardless of the actual duration of the use of the anchor drug in the OBT. If a patient starts maraviroc during the study, the follow up time accrued before starting maraviroc will be applied to the “maraviroc-unexposed” group and the follow up time accrued after starting maraviroc will be applied to the “maraviroc-exposed” group.

For the maraviroc unexposed group, the anchor drug in the OBT regimen is identified according to the following hierarchy:

- ▶ Raltegravir or other integrase inhibitor
  - ▶ Enfuvirtide or other fusion inhibitor
    - ▶ Etravirine or other second generation NNRTI
      - ▶ Darunavir or other protease inhibitor

The following are the currently commercially available drugs in each class at the time of the finalization of the SAP:

Protease Inhibitors (PI):

- ▶ tipranavir, indinavir, saquinavir, lopinavir, fosamprenavir, ritonavir, darunavir, atazanavir, nelfinavir

Nucleoside/Nucleotide Reverse Transcriptase Inhibitors (NRTI):

- ▶ emtricitabine, lamivudine, zalcitabine, zidovudine, didanosine, tenofovir disoproxil fumarate, stavudine, abacavir

Non-Nucleoside Reverse Transcriptase Inhibitors (NNRTI):

- ▶ delavirdine, efavirenz, nevirapine, etravirine

Fusion Inhibitors:

- ▶ enfuvirtide

Entry Inhibitors:

- ▶ maraviroc

Integrase Inhibitors:

- ▶ raltegravir

Patients starting CCR5 inhibitors other than maraviroc: In both groups, follow up will be terminated if a patient starts using any CCR5 inhibitor (either experimental or commercially available) other than maraviroc.

Patients switching to a non-participating physician: If the patient does not withdraw consent, follow up will continue. In these cases, only the mortality endpoints will be collected via direct patient contact by a CRO.

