## 6. ENDPOINTS AND COVARIATES

### 6.1. Study Endpoint(s)

The study endpoints are:

1. Centers for Disease Control and Prevention Category C AIDS-defining opportunistic infections will be considered as study end points up to 6 months post-discontinuation of maraviroc or the anchor drug in the OBT ([Appendix 1](#)). After 6-months, these clinical events will be handled as AE.
2. All malignancies up to five years of follow-up will be considered as study endpoints.
3. Liver failure will be considered as study endpoints up to 6 months post-discontinuation of maraviroc or the anchor drug in the OBT. After 6-months, these clinical events will be handled as AE.

4. Myocardial infarction or ischemia up to five years of follow-up will be considered as study endpoints.
5. Death from liver-related cause up to five years of follow-up will be considered as study endpoints.
6. Death from any cause up to five years of follow-up will be considered as study endpoints.

In addition, the following will be considered as study end points up to 6 months post-discontinuation of maraviroc or the anchor drug in the OBT:

- viral encephalitis
- rhabdomyolysis

After 6-months, these clinical events will be handled as AE.

The operational diagnostic criteria of each endpoint are described in the endpoint adjudication manual for this study.

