## 8.2. Safety Analyses

All safety data will be subjected to clinical review and summarized according to Pfizer Data Standards and using the Safety Analysis Set. The format and algorithms described in Pfizer Data Standards documentation will be followed to produce summary tables and listings.

This study will provide data to calculate incidence rates on each of the study endpoints in the two study groups and will be analyzed as given below:

1. Descriptive statistics (ie, frequency, percent, mean, median, standard deviation as appropriate depending on data type) will be used to summarize characteristics (clinical and demographic) of patients enrolled in the study. (Potential variables include but are not limited to age, gender, weight, BMI, race, smoking classification, alcohol use (yes/no), HIV-1 RNA level, CD4+ T lymphocyte counts, duration of antiretroviral therapy, duration of HIV infection, number of failed regimens etc.).
2. Cumulative incidence rates and incidence-density rates of the study endpoints in the two groups will be reported along with respective 95% confidence intervals.
3. Subject discontinuation, loss to follow-up and total person-time of follow-up accrued in the study will be summarized.
4. Depending on data availability, appropriate subgroup analyses may be performed to further describe the rates of the study endpoints stratified by age group, gender, baseline CD4+ cell counts, baseline viral load, hepatitis C/hepatitis B serology, duration of maraviroc use, total duration of antiretroviral use, components of OBT etc.
5. In addition to the study endpoints, SAEs and drug-related adverse reactions reported during the study will be summarized in tables and listings.

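### SAP 4.2.2 keeps patients who move to a non-participating physician in follow-up for mortality only, Protocol 6.5 discontinues them, and no current text ends their person-time for the other endpoints

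*SAP*

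**What the plan says.** **SAP 4.2.2**, on patients who move to a non-participating physician: "If the patient does not withdraw consent, follow up will continue". It then limits what is gathered: "In these cases, only the mortality endpoints will be collected via direct patient contact by a CRO". Earlier in the section, for each enrolled group, "all follow up time accrued in the study will be contributed to the" group concerned, however long the drug was taken.

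**Protocol 6.5**, on the same patients: if "a patient switches to a physician who is not participating in the study, the patient will be discontinued from the study". The enrolling physician completes a "follow up questionnaire with the last available clinical data and the subject summary module of the questionnaire". Unless consent is withdrawn, vital status is then sought in the manner of Protocol 6.4. Section 6.4 keeps un-adjudicated deaths out of the primary analyses.

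**What bounds the endpoints.** SAP 6.1 states: "Myocardial infarction or ischemia up to five years of follow-up will be considered as study endpoints". Malignancy has the same bound. Opportunistic infection (OI), viral encephalitis, liver failure and rhabdomyolysis are bounded only by six months after stopping maraviroc or the anchor drug.

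**Where the person-time is used.** SAP 8.2, item 2: "Cumulative incidence rates and incidence-density rates of the study endpoints in the two groups will be reported along with respective 95% confidence intervals". SAP 3 carries this into the yearly reports to regulators: "The analyses as outlined in Section 8.2 will be adopted for reporting these results".

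**The concern.** An incidence-density rate is sound only if events could be counted during all the time in its denominator. For switchers the SAP stops collecting every endpoint except death but says that follow-up goes on, and it has a general rule crediting accrued time to the group. Nothing separates time at risk for death from time at risk for the other endpoints.

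The absolute rates are a main product of this study. Objectives 1 and 2 are estimates of rates, Objective 4 compares them with an external cohort, and SAP 4.1 states no hypotheses. Extra event-free time pushes these rates one way, downward, which in a safety study is the reassuring direction.

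The mortality endpoints have a related gap. SAP 4.2.2 collects switchers' deaths through direct contact. Protocol 6.5 points to 6.4, where un-adjudicated deaths stay out of the primary analyses, although the reach of that rule to switchers is by inference. Protocol 7.4 has the Endpoint Committee adjudicate from medical records, which direct contact does not by itself supply. It is therefore unclear which deaths go with which person-time.

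**Working it through.** **1. Do other passages settle the conflict?**
- Protocol 6.6 lists the events that end follow-up; a change of physician is not among them.
- Protocol 9 lets the SAP modify the protocol's plans, so Protocol 6.5 does not prevail by default.
- Protocol 7.4 lets other treating physicians report endpoints to the enrolling physician, but SAP 4.2.2 limits collection for switchers to mortality.
- Protocol 7.4 also plans a registry search for malignancies where local law and access allow. This can recover some malignancies but none of the other endpoints.

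None of these gives a censoring date.

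**2. Reproduce the planned denominator** (Appendix 3, Scenario 1: 1,500 per arm, 10% lost each year, at mid-year).

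PY = Σ 1,500 × 0.9^(y−1) × 0.95, y = 1 to 5
= 1,425 + 1,282.5 + 1,154.25 + 1,038.83 + 934.94 = 5,835.5

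The plan states 5,835 (Appendix 3) and 5,836 (sample size text), so it reproduces. With the 3.5 per 1,000 of Protocol 9.1, expected myocardial infarctions (MI) are 3.5 × 5.835 = 20.4, matching the 20 in Table 2. The SAP text as available reads 5 per 1,000, which would give 29.2 and does not fit Table 2, so I use 3.5.

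**3. Add switchers' later time.** Let s be the share of the annual loss who are switchers kept in follow-up. The documents give no value, so s = 10%, 25% and 50% are assumptions. With no loss at all, PY = 1,500 × 5 = 7,500, so all lost time is 7,500 − 5,835 = 1,665.

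Kept to year 5: PY(s) = 5,835 + 1,665s. Recorded MI rate = 3.5 × 5,835 / PY(s).

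| s | PY(s) | Multiplier | MI rate per 1,000 |
|---|---|---|---|
| 10% | 6,002 | 0.972 | 3.40 |
| 25% | 6,251 | 0.933 | 3.27 |
| 50% | 6,668 | 0.875 | 3.06 |

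If switchers are themselves lost at 10% a year after the switch year, PY is 5,982, 6,202 or 6,569 and the MI rate 3.41, 3.29 or 3.11.

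**4. Compare with sampling error.** The exact Poisson 95% interval for 20 events in 5,835 PY is 2.09 to 5.29 per 1,000. All the shifts lie inside it.

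**5. Internal rate ratio.** The ratio is multiplied by (multiplier, exposed) / (multiplier, unexposed). Equal switching gives 1. With 50% in the exposed arm and 25% in the unexposed, it is 0.875 / 0.933 = 0.94; reversed, 1.07. Nothing in the documents says that switching differs.

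**6. On-drug endpoints.** Changing physician is not stopping the drug, so while the drug continues the same dilution applies. The size cannot be fixed. Rebuilding Scenario 2 from its stated rates gives 2,804 to 3,068 PY depending on timing choices, none equal to the stated 2,875. Moreover, the drug-stop date, which closes the six-month window, is not collected after a switch.

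**The case against.** The strongest reply is that the sentence on accrued time only assigns time to exposure groups and does not define risk time for each endpoint. On that view, continued follow-up in SAP 4.2.2 means mortality follow-up; a patient discontinued under Protocol 6.5 accrues no more study time; and the Kaplan-Meier and Cox analyses in SAP 8.2 would ordinarily censor when an endpoint is no longer observed. A careful programmer could reach the right result.

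This is a fair reading, and it limits the point: dilution is possible, not planned. It does not remove the point, because the SAP does not state that reading and no current passage gives the date. A censoring rule for switchers does appear in the Amendment 1 log (Protocol Appendix 4), but that is superseded text and cannot be treated as in force.

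Two further objections stand in full. The size rests on assumed switching shares. And no percentage should be attached to OI: the drug-stop date is unobserved, the planned person-time could not be rebuilt, and Protocol 9.2 expects recurrent events, so a simple Poisson interval would understate the uncertainty.

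A reader might go further and infer that the plan commits to biased rates, or that the comparison of maraviroc with the internal comparator is biased. The documents support neither. The first needs the literal reading; the second also needs differential switching, of which there is no sign.

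**Conclusion.** The point holds as a conflict between the SAP and the protocol, with an unstated censoring date. On the literal SAP reading, absolute non-mortality rates are understated. For MI the understatement is about 3%, 7% or 12.5% if switchers make up 10%, 25% or 50% of the planned loss and are kept to year 5, and somewhat less if they are later lost. These shares are assumptions, and every resulting MI rate stays within sampling error on 20 events. Malignancy is affected where no registry search is made. For OI, viral encephalitis, liver failure and rhabdomyolysis the direction is the same while the drug continues, but the size is not established. For deaths, the pairing of events and person-time is undefined. Severity is low to moderate: the likely effect is modest, but it feeds Objectives 1, 2 and 4 and the yearly regulatory reports, and the correction is cheap.

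**What to change.** Amend SAP 4.2.2 so that it agrees with Protocol 6.4 and 6.5:

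1. **Non-mortality endpoints.** For MI/ischemia, OI, viral encephalitis, liver failure, rhabdomyolysis, and malignancy found through active follow-up, end a switcher's person-time at the last clinical encounter with the participating physician. Analyse malignancies found through the registry search of Protocol 7.4 separately, with person-time matched to registry coverage.
2. **Deaths.** In the primary analysis of all-cause and liver-related death, count only adjudicated deaths and end switchers' person-time at that same encounter. Put later un-adjudicated deaths in a supplementary all-cause mortality analysis, with person-time running to the last known vital-status date.

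The cost is a few sentences in the SAP and slightly fewer person-years than the literal reading would give. No new data collection is needed.

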#### 4.2.3. Survival Bias

It is anticipated that up to 15% of the patients in the maraviroc-exposed group will comprise of patients who started maraviroc prior to enrollment in this study as participants in the maraviroc expanded access program (A4001050) and are still continuing the drug. The exact therapy start date and baseline covariates for these patients are documented in the A4001050 study database and will be used. Appropriate statistical analytical techniques (Muñoz, Wang et al. 1989; Hoover, Muñoz et al. 1991; Tarwater, Mellors et al. 2001; Cole, Li et al. 2004) that account for staggered entry of exposed subjects into study will be utilized to address the theoretical concern of survival bias from enrolling patients who were already exposed to the drug at study entry. In addition, sensitivity analyses will be performed to determine whether inclusion of such subjects substantially alters the findings of this study and the results will be reported.

The study will not enroll patients who started maraviroc in regular clinical practice outside of a clinical study since reliable data on the date of first exposure and baseline characteristics at that time may not be consistently available. Also, the study will not enroll into the maraviroc-unexposed arm any individual with prior exposure to maraviroc.

#### 4.2.4. Scientific Steering Committee

A Scientific Steering Committee (SSC) with external experts from epidemiology, biostatistics, infectious disease/HIV medicine, hepatology, cardiology, and oncology will be constituted for this study. The role of this external body is (1) to safeguard the interests of study participants and (2) to monitor the study conduct, in conjunction with the sponsor study team. The remit of the SSC will be described in the charter for the SSC. In summary, the role of the SSC will be to monitor the progress of the study on a regular basis, including logistical and operational aspects, to establish acceptable performance criteria (eg, acceptable rates of withdrawn consent and loss to follow-up), to evaluate the quality of the data being collected in the study, and to assist the sponsor in the development of any remedial plans of action as necessary. In the event of recommendations for a significant change (eg, study stoppage) by the SSC due to safety issues, Pfizer will notify regulatory agencies where necessary, as per legal or regulatory requirements.

#### 4.2.5. Endpoint Committee

The Endpoint Committee (EC) will review in a blinded manner all study endpoints occurring over the course of the study. The EC will be comprised of an independent group of infectious disease specialists, hepatologists, cardiologists and oncologists experienced in the treatment of HIV-1 infection and/or the study of HIV in large observational study settings. The members of the EC will receive de-identified data gathered on subjects who are suspected to have experienced a study outcome and will be responsible for adjudicating and

coding the endpoints. Details of these activities are described in greater detail within the endpoint adjudication manual for the study.

## 5. ANALYSIS SETS

All tables and figures will be based on the safety analysis set population as described below.

### 5.1. Full Analysis Set

Same as in Section 5.3: *Safety Analysis Set*.

### 5.2. Per Protocol Analysis Set

None

### 5.3. Safety Analysis Set

All subjects who enroll in the study will be included in the safety analyses and listings.

### 5.4. Other Analysis Sets

None

### 5.5. Treatment Misallocations

Not applicable.

### 5.6. Protocol Deviations

If applicable, a full list of protocol deviations will be compiled and reviewed to identify major and minor deviations prior to official database release.

## 6. ENDPOINTS AND COVARIATES

### 6.1. Study Endpoint(s)

The study endpoints are:

1. Centers for Disease Control and Prevention Category C AIDS-defining opportunistic infections will be considered as study end points up to 6 months post-discontinuation of maraviroc or the anchor drug in the OBT ([Appendix 1](#)). After 6-months, these clinical events will be handled as AE.
2. All malignancies up to five years of follow-up will be considered as study endpoints.
3. Liver failure will be considered as study endpoints up to 6 months post-discontinuation of maraviroc or the anchor drug in the OBT. After 6-months, these clinical events will be handled as AE.

4. Myocardial infarction or ischemia up to five years of follow-up will be considered as study endpoints.
5. Death from liver-related cause up to five years of follow-up will be considered as study endpoints.
6. Death from any cause up to five years of follow-up will be considered as study endpoints.

In addition, the following will be considered as study end points up to 6 months post-discontinuation of maraviroc or the anchor drug in the OBT:

- viral encephalitis
- rhabdomyolysis

After 6-months, these clinical events will be handled as AE.

The operational diagnostic criteria of each endpoint are described in the endpoint adjudication manual for this study.

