2. STUDY OBJECTIVES AND ENDPOINTS

2.1. Objectives

1. To estimate the incidence rates of: (a) Centers for Disease Control and Prevention category C AIDS-defining opportunistic infections (OI), (b) viral encephalitis, (c) liver failure, and (d) rhabdomyolysis in treatment-experienced HIV-1 infected patients receiving maraviroc during time of use and for up to six months following discontinuation of maraviroc treatment, up to a total of five years since entry into the study.
2. To estimate the incidence rates of (a) myocardial infarction (MI) or ischemia, (b) all malignancies, (c) all cause mortality, and (d) liver related deaths in treatment-experienced HIV-1 infected patients receiving maraviroc for up to five years after entry into the study regardless of the actual duration of maraviroc use.
3. To compare the rates of the study endpoints in patients receiving maraviroc to those observed in an internal comparator group of treatment-experienced, HIV-1 infected patients not receiving maraviroc.
4. To compare the observed rates of the study endpoints in patients receiving maraviroc in this study to those observed in HIV-1 infected patients not receiving maraviroc in an appropriate external comparator cohort (eg, EuroSIDA).

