6.3. Follow-up of patients discontinuing maraviroc

If a patient discontinues maraviroc, the enrolling physician will record information on the date of and primary reason for discontinuation. Discontinuation of maraviroc due to adverse events should be distinguished from discontinuation due to insufficient response, and any serious adverse events (SAE) should be reported immediately to Pfizer, as the Sponsor's designated representative. A change in any of the components of OBT will not be considered as treatment discontinuation if the patient continues to receive maraviroc, but these changes in regimen will be recorded on patient questionnaires by enrolling physicians. Follow-up will continue after a patient discontinues maraviroc up to a total period of 5 years since enrollment, and safety data will be collected and reported for a total of 5 years following enrollment as well.

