Study endpoints that are closely temporally related to drug exposures ie, CDC category C opportunistic infections, viral encephalitis, rhabdomyolysis and liver failure will cease to be adjudicated as study endpoints after six months following discontinuation of maraviroc. For patients in the maraviroc unexposed comparator group, adjudication of these events will cease after six months following discontinuation of the anchor drug in their OBT as identified at baseline (Section 7.2). If these events are diagnosed after this cut-off period, they will be considered as any other adverse event and reported per the Adverse Event Reporting guidelines described in Section 8, which requires the collection and reporting of all serious adverse events (SAE) and all adverse reactions. Occurrence of myocardial infarction or ischemia, malignancies, and death (all-cause and liver-related) will be reported and adjudicated as study endpoints for up to five years following enrollment.

The follow-up duration for malignancies may be extended beyond five years if, based on emerging safety data, the Scientific Steering Committee (SSC) overseeing the study recommends a longer period of observation. Due to the potentially prolonged time required for a malignancy to become clinically apparent, a search of national and state cancer and death registries will be performed to look for all episodes of malignancy within 10 years of study entry for all subjects in countries where such registries are available, are accessible for research purposes and where such search is allowed by local law. Active study participation of subjects will be for only 5 years, but informed consent will be obtained at enrollment allowing for passive subject follow-up beyond the 5 years of active participation through this additional search of cancer and vital status registries. This search will be conducted by a designated CRO or professional search firm using appropriate national identifiers collected at enrollment. The investigators will not have to do the search.

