6. Crude and adjusted rate ratios with 95% confidence intervals will be calculated for each study endpoint comparing maraviroc-exposed patients to maraviroc-unexposed patients. Multivariate analysis techniques will be used as appropriate (e.g., Poisson regression model) to account for the baseline difference in the two study groups via propensity score technique. Specifically, since subjects are not randomized to treatment, there is a potential for imbalance in the above-mentioned important demographic and baseline characteristics between groups. To account for the imbalance between the two groups on the clinically important demographic and baseline characteristics, the confidence intervals will be adjusted for propensity score quintile. Specifically, propensity score for treatment membership (maraviroc exposed vs. maraviroc un-exposed) will be calculated for each subject from a logistic regression with the above mentioned covariates as predictors and study group membership as the outcome. Participants with similar propensity scores generally have similar distribution of the covariates on which the score is based. Participants will then be categorized into quintiles according to their propensity score. Four indicator variables will be created to represent the propensity score quintiles and will be used in the multivariate model as covariates along with the primary exposure variable i.e., exposure to maraviroc. Adjusting for propensity score quintile in this manner helps account for imbalances at baseline as discussed in D'Agostino (1998).
7. Appropriate survival analyses techniques (eg, Kaplan-Meier survival curves, Cox proportional hazards model) will be used to further analyze the data. The multivariate models will incorporate appropriate techniques referred to in section 4.2.3 to adjust for

potential survival bias.

8. In addition, incidence rates in patients receiving maraviroc in this study may be compared to those reported in comparable patients (ie, those with similar propensity scores and with the smallest Mahalanobis' distance between baseline values (D'Agostino, 1998) not using maraviroc in other HIV-1 infected cohort(s) such as EuroSIDA. The baseline characteristics of the patients (eg, number of failed regimens, CD4+ T lymphocyte counts) in this study will be used to identify comparable subjects from the external cohort(s).

The following data will be presented in standard safety summaries:

- *adverse events*

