#### **Expected person-time of observation in:**

These events will be adjudicated and analyzed as study endpoints if they occur during use of maraviroc or the anchor drug in the OBT, or within 6 months following their discontinuation

- Based on clinical experience, it is assumed that the rate of drug discontinuation will be higher in the earlier part of the study and will gradually decrease over time. To obtain a conservative estimate, it is assumed based on the observations from the 48-week clinical development program of maraviroc that the rate of discontinuation will be approximately 30% during the first 6 months of therapy, 25% between the 7th and 12th month, 20% between the 13th and 18th months and 15% in each 6 month period thereafter. For the purpose of this calculation it is assumed that on average discontinuation occurs at the midpoint of each 6-month period.

- It is assumed that 5% of the patients (either continuing maraviroc or during the 6 months post discontinuation follow-up) will be lost every 6 months and on average these losses will occur at the midpoint of the 6-month period.
- Patients lost to follow-up during any 6-month period (either on or off maraviroc) will contribute only 3 months of follow-up time during that period. Patients who are being actively followed up at the end of each 6-month period will contribute 6 months of follow-up time.

Based on the above assumptions, both these groups will accrue 2875 person-years of follow-up during the study for the assessment of AIDS-defining OI, viral encephalitis, rhabdomyolysis and liver failure.

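### For OI, viral encephalitis, liver failure and rhabdomyolysis, one rate ratio pools on-drug time with the six months after stopping: it can move either way from 1 if stopping rates and post-stop risk both differ, and it dilutes an on-drug effect

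*SAP*

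**What the plan says.** SAP 6.1 item 1 states that category C opportunistic infections "will be considered as study end points up to 6 months post-discontinuation of maraviroc or the anchor drug in the OBT". The same limit applies to liver failure, viral encephalitis and rhabdomyolysis. Protocol 2.1, objective 1, defines the maraviroc rate the same way, in patients "receiving maraviroc during time of use and for up to six months following discontinuation of maraviroc treatment". Protocol 7.4 gives the comparator a parallel rule: "adjudication of these events will cease after six months following discontinuation of the anchor drug in their OBT as identified at baseline".

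The comparison is in SAP 8.2 item 6: "Crude and adjusted rate ratios with 95% confidence intervals will be calculated for each study endpoint comparing maraviroc-exposed patients to maraviroc-unexposed patients". Adjustment is by propensity-score quintiles built from the baseline covariates of SAP 6.2. No item divides follow-up into time on drug and time after stopping. The nearest is an optional subgroup by duration of maraviroc use (SAP 8.2 item 4), which has no comparator counterpart.

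On stopping, SAP Appendix 3 (Scenario 2) says "it is assumed based on the observations from the 48-week clinical development program of maraviroc that the rate of discontinuation will be approximately 30" per cent in the first six months. It then assumes 25%, 20% and 15% in later half-years and arrives at 2,875 person-years (PY) in each arm. Comparator anchor drugs may come from four classes (Protocol 7.2).

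SAP 4.2.2 credits all follow-up to the maraviroc-exposed "group regardless of the actual duration of maraviroc use" and, for the comparator, to the maraviroc-unexposed "group regardless of the actual duration of the use of the anchor drug in the OBT". It makes no exception for the four windowed endpoints.

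**The concern.** Time just after a stop need not carry the same risk as time on a stable regimen. Protocol 6.3 asks that "Discontinuation of maraviroc due to adverse events should be distinguished from discontinuation due to insufficient response", and either reason could go with a changed risk of the events counted here. Protocol 7.4 describes these four endpoints as closely tied in time to drug exposure.

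The share of an arm's window that is post-stop depends on how often its drug is stopped. If that share differs between arms and the post-stop rate differs from the on-drug rate, the pooled rates differ even when neither drug causes the events. Stopping happens after baseline, so propensity quintiles cannot remove this.

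There is a second consequence. An effect present only while the drug is taken is averaged with post-stop time and shrinks towards 1. This needs no difference in stopping between the arms. In a post-approval safety commitment, a single pooled ratio would not show which of these had occurred.

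**Working it through.** **Inputs from the documents.** 1,500 patients per arm. Stopping of 30%, 25%, 20% and then 15% per half-year, and 5% loss per half-year, both at mid-period (Appendix 3, Scenario 2). OI rate of 160 per 1,000 PY in the comparator (SAP 4.2.1). Detectable OI ratio of 1.1955 (Table 2).

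**Assumed, because the documents give no figure.** Comparator stopping at 0.5 to 1.5 times the Appendix 3 rates, with maraviroc stopping as in Appendix 3. Post-stop to on-drug rate ratio k from 0.5 to 3, the same in both arms.

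**1. Reproduce Scenario 2.** I used a ten-period life table. Stopping applies to those not lost, and each stopper adds 3 months of post-stop time in that period and 3 months in the next. On-drug time is 2,348 PY and post-stop time is 550 PY, in total 2,898 PY (plan: 2,875, a difference of +0.8%). The post-stop share is 550/2,898 = 19.0%. If loss and stopping are both taken from the starting number, the total is 2,804 PY and the share 20.0%.

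Events: 2,875 × 0.160 = 460, as in Table 2. For 460 events, a conditional binomial calculation with continuity correction gives 1.1955, also as in Table 2.

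**2. Null ratio with windowed person-time.** With on-drug rate r and post-stop share f, an arm's pooled rate is r[1 + f(k − 1)]. With no drug effect,

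ratio = [1 + f_M(k − 1)] / [1 + f_C(k − 1)], with f_M = 0.190 throughout.

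| Comparator stopping | Window PY | f_C | k = 0.5 | k = 1 | k = 1.5 | k = 2 | k = 3 |
|---|---|---|---|---|---|---|---|
| 0.5× | 4,055 | 0.091 | 0.948 | 1.000 | 1.047 | 1.090 | 1.166 |
| 0.75× | 3,411 | 0.140 | 0.973 | 1.000 | 1.023 | 1.044 | 1.078 |
| 1.0× | 2,898 | 0.190 | 1.000 | 1.000 | 1.000 | 1.000 | 1.000 |
| 1.25× | 2,488 | 0.241 | 1.029 | 1.000 | 0.977 | 0.959 | 0.931 |
| 1.5× | 2,161 | 0.294 | 1.061 | 1.000 | 0.955 | 0.920 | 0.869 |

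Within each state the ratio is 1.000 in every cell.

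**3. Chance that the 95% interval excludes 1 under no effect (OI).** Comparator pooled rate held at 160 per 1,000 PY, standard error of the log ratio = √(1/E_M + 1/E_C), where E_M and E_C are expected events. At 0.75× and k = 2 the chance is 11%. At 0.5× it is 12%, 31% and 75% for k = 1.5, 2 and 3. At 1.5× and k = 3 it is 48%, with the ratio below 1.

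**4. Dilution with equal stopping.** Take an on-drug ratio of 1.1955, no carry-over (post-stop ratio 1) and k = 1. Pooled ratio = 0.810 × 1.1955 + 0.190 = 1.158. With 460 comparator events, the standard error is √(1/460 + 1/(460 × 1.158)) = 0.0636. Power = Φ(ln 1.158/0.0636 − 1.96) = 64%. The same formula at 1.1955 gives 81%.

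On-drug time alone has 0.810 × 460 = 373 comparator events. The standard error is √(1/373 + 1/(373 × 1.1955)) = 0.0702 and power is about 72%. The split therefore recovers part of the loss.

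**5. SAP 4.2.2 read literally.** Suppose the denominator is all follow-up (5,835 PY per arm) while events stop counting six months after a stop. At k = 1 the null ratio is then the ratio of window PY: 2,898/4,055 = 0.715 at 0.5×, 0.85 at 0.75×, 2,898/2,488 = 1.165 at 1.25×, and 2,898/2,161 = 1.341 at 1.5×.

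**6. What a split can support.** At the planning rates, 550 post-stop PY give 0.160 × 550 = 88 OI per arm, but only 0.0035 × 550 = 1.9 liver failures. The documents assume no rate for encephalitis or rhabdomyolysis.

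**The case against.** A reader might infer that unequal stopping alone pushes the ratio away from 1. With windowed person-time it does not, as the k = 1 column shows. The second condition, a different rate after stopping, has no figure in either document, and the plan uses a single OI rate. Nor can one infer that the bias runs against maraviroc: the sign depends on which arm stops more and on whether k is above or below 1. The 75% false-positive figure needs both halved comparator stopping and a threefold post-stop rate, and the documents support neither.

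The window is also a deliberate choice, written into objective 1 and mirrored in the comparator. It is not an error. If a drug's toxicity or insufficient response causes the stop, a higher pooled rate is arguably partly a consequence of treatment, so describing it as arising without a drug effect can be disputed.

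Finally, the SAP does not state the windowed denominator used here. On the literal text of 4.2.2, the 0.5× scenario gives ratios below 1 even at k = 2 and 3 (0.78 and 0.83).

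All of this stands as a limit on the claim. It does not remove the gap. No planned output lets a reader see how much of each arm's window is post-stop, or whether the OI ratio differs between states. The general summaries of person-time and discontinuation, and of stops due to adverse events, do not link events to state. The dilution in step 4 needs neither unequal stopping nor a raised post-stop rate.

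**Conclusion.** The point holds in conditional form and justifies a modest change. Distortion without a drug effect requires both unequal stopping and a post-stop rate that differs from the on-drug rate. Over the assumed ranges the OI null ratio lies between about 0.87 and 1.17, against a detectable ratio of 1.1955. Dilution rests on the plan's own stopping rates plus the assumption of no carry-over: 1.1955 becomes about 1.16, with power of about 64%. All sizes are for OI. For the three rarer endpoints, size and direction are unknown. The conflict between SAP 4.2.2 and the six-month window is a separate and potentially larger problem, because under 4.2.2 unequal stopping is enough to move the ratio. It has to be settled first.

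**What to change.** 1. Reconcile SAP 4.2.2 with SAP 6.1 and Appendix 3, so that these four endpoints use person-time up to six months after stopping maraviroc or the anchor drug.
2. Keep the pooled ratio in SAP 8.2 item 6 as the main result.
3. Add to item 6 a supportive table by arm: events, assigned by onset date, and person-years, each divided into on drug and 0 to 6 months after stopping. For OI, give the on-drug and post-stop rate ratios with 95% intervals. For liver failure, viral encephalitis and rhabdomyolysis, give counts and person-years only.

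The cost is SAP wording and a small program, since medication use is already recorded at follow-up (Protocol 7.3). The drawback is that drug state is a post-baseline variable that treatment may affect, and an event that prompts a stop can fall on either side of the stop date. The split therefore stays supportive, and a pooled model adjusted for state should not become a main result.
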